8.2.2.3. Refraction

Refraction will be performed for each eye at Visit 1 (Screening). At Visits 2 to 4, if more than 10 letters in BCVA were lost compared to the screening visit, then refraction should be performed again.

8.2.2.4. Best-Corrected Visual Acuity

Best-Corrected Visual Acuity (BCVA) will be measured for each eye prior to the 08:00 (± 60 min) IOP measurement at all visits except for Visit 1 (Screening) and Visit 1a (optional, mid-washout visit). For Visit 1 (Screening) and Visit 1a (optional, mid-washout visit), BCVA will be performed prior to IOP measurement. BCVA will be measured under normal room illumination using visual acuity chart (ETDRS chart) and the logMAR scoring will be recorded in the subject's source document. The following procedure should be followed using ETDRS chart for BCVA testing.

8.2.2.4.1. ETDRS Visual Acuity Scoring

The Examiner records each letter identified correctly by circling the corresponding letter on an appropriate visual acuity worksheet. The Examiner records a letter read incorrectly, or a letter for which the subject made no guess, by crossing the letter out with an "x" or a line. Each letter read incorrectly is scored as one point. The last line in which a letter is read correctly will be taken as the Base logMAR line.

The total number of letters that have an “x” or a line through them (letters read incorrectly or not at all) down to and including the Base logMAR line, and multiply the total number by 0.02. Add this value to the Base logMAR value to obtain the logMAR score.

Example:

Subject correctly reads 4 of 5 letters on the +0.2 line, and 2 of 5 letters on the +0.1 line, and zero letters on the 0.0 line

Base logMAR value = +0.1 (last line in which a letter was read correctly)

Total number of letters missed = 4 (number of letters missed on the +0.2 line plus the number missed on the +0.1 line)

LogMAR score = +0.1 + (4 x 0.02) = 0.18

Table 6: LogMAR Scoring Grid for ETDRS Eye Chart

		Total Number of Letters Missed										
Snellen	Base LogMAR	0	1	2	3	4	5	6	7	8	9	10
20/200	+1.0	1.00	1.02	1.04	1.06	1.08	---	---	---	---	---	---
20/160	+0.9	0.90	0.92	0.94	0.96	0.98	1.00	1.02	1.04	1.06	1.08	1.10
20/125	+0.8	0.80	0.82	0.84	0.86	0.88	0.90	0.92	0.94	0.96	0.98	1.00
20/100	+0.7	0.70	0.72	0.74	0.76	0.78	0.80	0.82	0.84	0.86	0.88	0.90
20/80	+0.6	0.60	0.62	0.64	0.66	0.68	0.70	0.72	0.74	0.76	0.78	0.80
20/63	+0.5	0.50	0.52	0.54	0.56	0.58	0.60	0.62	0.64	0.66	0.68	0.70
20/50	+0.4	0.40	0.42	0.44	0.46	0.48	0.50	0.52	0.54	0.56	0.58	0.60
20/40	+0.3	0.30	0.32	0.34	0.36	0.38	0.40	0.42	0.44	0.46	0.48	0.50
20/32	+0.2	0.20	0.22	0.24	0.26	0.28	0.30	0.32	0.34	0.36	0.38	0.40
20/25	+0.1	0.10	0.12	0.14	0.16	0.18	0.20	0.22	0.24	0.26	0.28	0.30
20/20	0.0	0.00	0.02	0.04	0.06	0.08	0.10	0.12	0.14	0.16	0.18	0.20
20/16	-0.1	-0.10	-0.08	-0.06	-0.04	-0.02	0.00	0.02	0.04	0.06	0.08	0.10
20/12.5	-0.2	-0.20	-0.18	-0.16	-0.14	-0.12	-0.10	-0.08	-0.06	-0.04	-0.02	0.00
20/10	-0.3	-0.30	-0.28	-0.26	-0.24	-0.22	-0.20	-0.18	-0.16	-0.14	-0.12	-0.10

8.2.2.5. Slit-lamp Biomicroscopy

As described below, slit-lamp biomicroscopy examinations will be performed and graded immediately prior to the 08:00 (± 60 min) IOP measurement at all visits except for Visit 1 (Screening) and Visit 1a (optional, mid-washout visit). For Visit 1 (Screening) and Visit 1a (optional, mid-washout visit), the biomicroscopy examinations should be performed prior to IOP measurement. Some exception can be applied, if pupil dilation is required for evaluation. For example, the possible tear(s) in the posterior lens capsule. The slit-lamp exam for posterior lens capsule can be performed after the pupil dilation, that is at 16:00 after IOP measurement.

Anterior chamber cells and flare will be observed and graded using the Standardization of Uveitis Nomenclature (SUN) scale, before fluorescein instillation.

Anterior Chamber Cells

- (0) = No cells
- (0.5) = 1-5 cells
- (1) = 6-15 cells
- (2) = 16-25 cells
- (3) = 26-50 cells
- (4) = >50 cells

Anterior Chamber Flare

- (0) = None
- (1) = Faint
- (2) = Moderate (iris/lens details clear)
- (3) = Marked (iris/lens details hazy)
- (4) = Intense (fibrin/plastic aqueous)

The lid, conjunctiva, cornea, lens, and iris will be observed and graded on a 4-point scale (0-3 scale).

Lid Hyperemia

- None (0) = Normal
- Mild (1) = Redness of most or all the lid(s) margin OR skin
- Moderate (2) = Redness of most or all the lid(s) margin AND skin
- Severe (3) = Marked diffuse redness of both lid(s) margin AND skin

Lid Edema

- None (0) = Normal
- Mild (1) = Localized to a small region of the lid(s)
- Moderate (2) = Diffuse, most or all the lid(s) but not prominent/protruding
- Severe (3) = Diffuse, most or all the lid(s) AND prominent/protruding

Conjunctival (Palpebral and Bulbar) Hyperemia

- None (0) = Normal
- Mild (1) = Slight localized injection

Moderate (2) = Pink color, confined to palpebral OR bulbar conjunctiva

Severe (3) = Red color of the palpebral AND/OR bulbar conjunctiva

Conjunctival Chemosis

None (0) = Normal

Mild (1) = Slight localized swelling

Moderate (2) = Mild/medium localized swelling or mild diffuse swelling

Severe (3) = Moderate diffuse swelling

Corneal Edema

None (0) = Normal

Mild (1) = Mild, diffuse stromal haze

Moderate (2) = Dense, diffuse stromal haze or bullae

Severe (3) = Dense, diffuse bullae or stromal haze AND stromal edema

Corneal Staining (with fluorescein)

None (0) = Normal

Mild (1) = Localized, occasional punctate staining

Moderate (2) = Localized, dense OR diffuse occasional punctate staining

Severe (3) = Diffuse, dense punctate staining which may be confluent staining

Keratic Precipitate

None (0) = Normal

Mild (1) = Slight pigmentation or keratic precipitate

Moderate (2) = Moderate pigmentation or keratic precipitate

Severe (3) = Dense pigmentation or keratic precipitate

Lens

The lens will be noted as phakic, aphakic, or pseudophakic. Phakic lens will be graded as described below:

None (0) = No lens discoloration nor opacification

Mild (1) = Yellow lens discoloration or small lens opacity (axial or peripheral)

Moderate (2) = Amber lens discoloration or medium lens opacity (axial or peripheral)

Severe (3) = Brunescence lens discoloration or complete lens opacification (no red reflex)

Anterior Synechiae of Iris

None (0) = No anterior synechiae of iris is found

Mild (1) = <25% anterior synechiae of iris is found
Moderate (2) = 25% to 50% anterior synechiae of iris is found
Severe (3) = >50% anterior synechiae of iris is found

Posterior Synechiae of Iris

None (0) = No posterior synechiae of iris is found
Mild (1) = <25% posterior synechiae of iris is found
Moderate (2) = 25% to 50% posterior synechiae of iris is found
Severe (3) = >50% posterior synechiae of iris is found

8.2.2.6. Pachymetry (Central Corneal Thickness)

The central corneal thickness (μm) of each eye using any pachymeter including optical pachymeter, ultrasound pachymeter, OCT (optical coherence tomography) etc. will be measured and recorded after IOP measurement at Visit 1 (Screening). Pachymetry should be performed after IOP measurement. The same pachymeter should be used during the course of the study.

8.2.2.7. Gonioscopy

Gonioscopy will be performed to examine the angle of the anterior chamber after IOP measurement at Visit 1 (Screening), if it has not been performed within 3 months (90 days). The Shaffer scale will be used to rate the degree of angle closure.

(0) = approximately 5 degrees or less, complete or partial closure
(1) = approximately 10 degrees
(2) = approximately 20 degrees
(3) = approximately 30 degrees
(4) = approximately 40 degrees or more

8.2.2.8. Visual Field

Visual field examinations will be performed using a static or dynamic perimeter (Humphrey or Octopus) without pupil dilation at Visit 1 (Screening), if this has not been performed within 3 months (90 days) or the previous visual field test(s) indicates low subject reliability (e.g., due to fixation losses, false positive errors, or false negative errors). Glaucomatous visual field loss will be evaluated by the Investigator as presence or absence (mean deviation, pattern SD, glaucoma hemifield test, and type of glaucomatous visual field loss).

Visual field tests that, in the Investigator's opinion, indicate low subject reliability (e.g., due to fixation losses, false positive errors, or false negative errors) should be excluded. A copy of the computer printout from the visual field test(s) will be attached to the subject's source documents.

8.2.2.9. Ophthalmoscopy (Fundus) Examination

The ophthalmoscopy (fundus) examination will be performed for each eye at Visit 1 (Screening), Visit 2 (Baseline, Day 1), and Visit 4 Study Exit/Early Termination, and graded as described

below. Ophthalmoscopy will be performed under dilation at Visit 1 (Screening) and Visit 4 Study Exit/Early Termination. Pupil dilation must be performed after all other ocular procedures have been completed. Cup to disc ratio and abnormality in retina, macula, choroid, and vitreous will also be evaluated.

Glaucomatous Optic Nerve Findings

The optic nerve will be evaluated using a 4-point scale (0-3 scale).

- None (0) = No damage
- Mild (1) = Optic nerve damage, secondary to glaucoma including any rim loss (sloping or thinning)
- Moderate (2) = Optic nerve damage, including cupping to disc margin at one or more points
- Severe (3) = Optic nerve damage, nearly total cupping, only nasal rim or less present

8.2.2.10. Events of Special Interest (ESIs)

Events of Special Interest (ESIs) are medical events both anticipated and unanticipated that may have particular impact on the benefit/risk profile of DE-117 and therefore may require more detailed characterization. The DE-117 ESIs are as follows:

- Pregnancy:
 - There are no controlled data with the investigational product in human pregnancy. It is required that females of childbearing potential use effective contraception during the study and recommended for 4 weeks for female subjects of childbearing potential and 12 weeks for male subjects capable of fathering children after the completion of the study. Any pregnancy occurring during study treatment should be reported and the subject will be discontinued from the study. The subject should be followed until the end of pregnancy or until the end of the study, whichever is longer.
- Medication administration errors
 - Study medication administration errors determined to be **significant** by the Investigator will be reported and evaluated as ESIs. Examples of study medication administration errors may include, but are not limited to: incorrect dose of study medication and administration of study medication from an incorrect kit. An AE does not necessarily need to have occurred to count as a study medication administration error. A medication administration error is an unintended failure in the process of treatment with a medicinal product that leads to, or has the potential to lead to harm of the subject.
- Macular edema (including cystoid macular edema):
 - Macular edema has been reported in some patients during the DE-117 clinical trials. Any cases of macular edema (including cystoid macular edema) should be reported in the ESI form in eCRF, or in case the Electronic Data Capture (EDC) system is down, in the manual ESI form. Any cases of macular edema (including

cystoid macular edema) will need to be followed until the event is determined to be resolved, irreversible, chronic, stable, the subject withdraws consent, or no further information can be reasonably obtained as per [Section 8.3.3](#).

Most ESIs are AEs, some ESIs may also be SAEs, and some ESIs may not be AEs (e.g., an IP administration error may not be an AE; pregnancies are not AEs). However, all ESIs should be reported within 24 hours of knowledge of the event using applicable eCRFs and recording as much information as available. ESIs should be followed by the investigator to the same extent as SAEs, that is, until the event is determined to be resolved, irreversible, chronic, stable, the subject withdraws consent, or no further information can be reasonably obtained. Monitoring for pregnancy and follow-up of pregnancy is described in [Section 8.3.5](#).

8.2.3. Other Assessments

8.2.3.1. Blood Sample for Pharmacogenomics/genomics Study

For sites which elect to participate and for subjects who agree to provide a blood sample, an exploratory biomarker laboratory research study will be performed to evaluate the association of possible genetic biomarkers with the study drug(s) and/or ophthalmologic conditions.

Approximately 10 mL of blood will be collected for genetic analysis from the subject and stored until shipment. Please refer to the separate procedure manual for sample handling, storage, and shipment. The samples will be coded to protect the subjects' private information. Nucleic acids will be extracted from blood sample and stored in the repository for future pharmacogenomics/genomics studies performed by appropriate assay platforms such as PCR (Polymerase Chain Reaction), hybridization, and sequencing on the genes involved in the study drug(s) and/or ophthalmologic conditions. Individual subjects' results from the research testing on their samples will not be communicated to them.

Samples collected and stored, and relevant documents (the list of screening/registration of subjects only for documents to be retained by the medical institution) will be retained for the period agreed in the ICF. Upon completion of analyses or the retention period, they will be anonymized and discarded. If the subject withdraws the consent, samples will be immediately disposed, and the applicable subject will be informed in writing.

For any other matters not specified in the protocol, a written procedure will be defined separately.

8.2.3.2. Pharmacodynamics

Pharmacodynamic parameters are not evaluated in this study.

8.2.3.3. Biomarkers

Biomarkers are not evaluated in this study.

8.2.3.4. Pharmacokinetics

PK parameters are not evaluated in this study.

8.2.4. Study Supplies

Commercial urine pregnancy test kits and customized blood sample collection kits for the pharmacogenomics/genomics will be provided by Santen (or designee).

8.3. Adverse Events and Serious Adverse Events

The definitions of an AE or SAE can be found in [Section 10.2](#).

AE will be reported by the subject (or, when appropriate, by a caregiver, surrogate, or the subject's legally authorized representative).

The investigator and any qualified designees are responsible for detecting, documenting, and recording events that meet the definition of an AE, SAE or ESI and remain responsible for following up AEs that are serious, considered related to the study intervention or study procedures, or that caused the subject to discontinue the study intervention (see [Section 7](#)).

8.3.1. Time Period and Frequency for Collecting AE and SAE Information

All SAEs will be collected from the signing of the ICF until the subject withdrawals or completes the scheduled exit visit.

All AEs will be collected from the signing of the ICF until the subject withdrawals or completes the scheduled exit visit.

All SAEs and ESIs will be recorded and reported to Santen or designee immediately and under no circumstance should this exceed 24 hours, as indicated in [Section 10.2](#). The investigator will submit any updated SAE or ESI data to Santen within 24 hours of it being available.

Investigators are not obligated to actively seek AE or SAE after conclusion of the study participation. However, if the investigator learns of any SAE, including a death, at any time after a subject has been discharged from the study, and he/she considers the event to be reasonably related to the study intervention or study participation, the investigator must promptly notify Santen.

8.3.2. Method of Detecting AEs and SAEs

The method of recording, evaluating, and assessing causality of AE, SAE and ESI and the procedures for completing and transmitting SAE reports are provided in [Section 10.2](#).

Care will be taken not to introduce bias when detecting AEs and/or SAEs. Open-ended and non-leading verbal questioning of the subject is the preferred method to inquire about AE occurrences.

8.3.3. Follow-up of AEs and SAEs

All reported AEs should be followed by the investigator until resolution or until the subject's participation in the study ends.

More extensive follow-up is required for (1) SAEs, (2) ESIs and (3) IP related AEs that lead to or cause early withdrawal of a subject from the study. All of these types of events should be followed by the investigator until the event is determined to be resolved, irreversible, chronic, stable, the subject withdraws consent, or no further information can be reasonably obtained. In

addition to the above, Santen (or designee) may request, on a case-by-case basis, follow up of events/subjects beyond the scheduled exit visit.

Prior to database lock, follow-up information on an individual SAE or AE (or ESI) will be entered into the eCRF. When database lock has already been completed, or if information requested by Santen is not part of the eCRF, the site's response to follow-up requests should be emailed or documented on paper and faxed to Santen Global Pharmacovigilance (see [Table 1](#)).

8.3.4. Regulatory Reporting Requirements for SAEs

Prompt notification by the investigator to Santen of a SAE is essential so that legal obligations and ethical responsibilities towards the safety of subjects and the safety of a study intervention under clinical investigation are met.

Santen has a legal responsibility to notify both the local regulatory authority and other regulatory agencies about the safety of a study intervention under clinical investigation. Santen will comply with country-specific regulatory requirements relating to safety reporting to the regulatory authority, IRB/IEC and investigators.

Investigator safety reports must be prepared for suspected unexpected serious adverse reactions (SUSAR) according to local regulatory requirements and sponsor policy and forwarded to investigators as necessary.

An investigator who receives an investigator safety report describing a SAE or other specific safety information (e.g., summary or listing of SAEs) from Santen will review and then file it along with the Investigator's Brochure and will notify the IRB/IEC, if appropriate according to local requirements.

8.3.5. Pregnancy

8.3.5.1. Female subjects who become pregnant

The investigator will collect pregnancy information on any female subject who becomes pregnant while participating in this study. Information will be recorded in eCRF and on the appropriate manual form and submitted to Santen within 24 hours of learning of a subject's pregnancy. The subject will be followed to determine the outcome of the pregnancy.

The investigator will collect follow-up information on the subject and the neonate and the information will be forwarded to Santen. Generally, follow-up will not be required for longer than 6 to 8 weeks beyond the estimated delivery date. Any termination of pregnancy will be reported, regardless of fetal status (presence or absence of anomalies) or indication for the procedure. While pregnancy itself is not considered to be an AE or SAE, any pregnancy complication or elective termination of a pregnancy will be reported as an Event of Special Interest (ESI). Abnormal pregnancy outcomes (e.g., spontaneous abortion, fetal death, stillbirth, congenital anomalies, ectopic pregnancy) are considered SAEs and will be reported as such.

Any post-study pregnancy-related SAE considered reasonably related to the IP by the investigator will be reported to Santen. While the investigator is not obligated to actively seek this information in former study subjects, he or she may learn of an SAE through spontaneous

reporting. Any female subject who becomes pregnant while participating in the study will discontinue IP and be withdrawn from the study.

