5.1. Inclusion Criteria

At Visit 1 (Screening), the subject must meet all of the following inclusion criteria:

1. Provide signed written informed consent on the IRB/EC approved ICF.
2. Be 18 years of age or older on the date of signing the ICF and able and willing to comply with all treatment and follow-up study procedures.
3. If a subject is a female of childbearing potential (i.e., not post-menopausal [within 12 months since the last menses] or not surgically sterile [less than 6 months]), she must have a negative urine pregnancy test and must use at least one of the following acceptable contraceptive methods during the study (as well as for 4 weeks following last dose in the study).
 - Abstinence
 - Hormonal contraceptive method (including oral or transdermal contraceptives, injectable progesterone, progestin subdermal implants, progesterone-releasing intrauterine devices [IUDs]) initiated at least 28 days prior
 - Placement of a copper-containing IUD
 - Condom with spermicidal foam/gel/film/cream/suppository
 - Vasectomized male partner (surgery at least 6 months prior)

Male subjects capable of fathering children should use/ practice an acceptable contraceptive method, such as abstinence, condom or vasectomy (surgery at least 6 months prior) or other contraceptive method deemed adequate by the investigator throughout the course of the study (as well as for 12 weeks following last dose in the study).

4. Subjects must have a diagnosis of POAG or OHT in both eyes, or one eye with POAG and the other with OHT.
5. BCVA of +0.60 logMAR (Snellen equivalent 20/80) or better in each eye.
6. Central corneal thickness $\geq 480 \mu\text{m}$ and $\leq 600 \mu\text{m}$ in each eye.
7. Anterior chamber angle grade ≥ 2 (Shaffer scale) in each eye.

In addition to continuing to meet inclusion criterion 5 (BCVA), the subject must meet the following criteria at Visit 2 (Baseline, Day 1):

8. Completed the required wait/washout period.

9. At all time points of IOP measurements (8:00, 12:00 and 16:00) at Visit 2 (Baseline, Day 1), have IOP of ≥ 22 mmHg in at least one eye (the same eye), and ≤ 34 mmHg in both eyes.

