8.3.5.2. Male subjects with partners who become pregnant

The investigator will attempt to collect pregnancy information on any male subject's female partner who becomes pregnant while the male subject is in this study. After obtaining the necessary signed informed consent from the pregnant female partner directly, the investigator will record pregnancy information on the appropriate form and submit it to Santen within 24 hours of learning of the partner's pregnancy.

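### Routine pregnancy collection stops at study exit, although the protocol's contraception periods run 4 weeks (women) and 12 weeks (men) past the last dose

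*Protocol*

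**What the plan says.** Collection of pregnancies is defined in three places in the protocol.

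- Section 8.3.5.1, women: "The investigator will collect pregnancy information on any female subject who becomes pregnant while participating in this study". The pregnancy is followed to its outcome, information on the neonate is collected, and the general limit is stated as "Generally, follow-up will not be required for longer than 6 to 8 weeks beyond the estimated delivery date".
- Section 8.3.5.2, men: the investigator will attempt to collect information on a "female partner who becomes pregnant while the male subject is in this study".
- Section 8.2.2.10, events of special interest (ESIs): "Any pregnancy occurring during study treatment should be reported and the subject will be discontinued from the study". It adds: "The subject should be followed until the end of pregnancy or until the end of the study, whichever is longer". The section closes by referring to Section 8.3.5 for the monitoring and follow-up of pregnancy.

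Contraception has a longer horizon. In criterion 3 of Section 5.1, repeated in Section 5.3.1, women must use it during the study "as well as for 4 weeks following last dose in the study", and men should use it during the study "as well as for 12 weeks following last dose in the study". Section 8.2.2.10 words the post-study part for both sexes as a recommendation and counts it from completion of the study.

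The last urine test and study exit are both at Visit 4 (Sections 8.1.5 and 8.2.2.2). The Schedule of Activities shows no later contact. After exit, Section 8.3.5.1 requires a report of a pregnancy-related SAE that the investigator considers reasonably related to the product, with no duty to look for one. Section 8.3.1 has a similar rule for SAEs in general. Section 8.3.3 lets the sponsor ask for follow-up beyond exit case by case.

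**The concern.** The sponsor has named pregnancy an ESI, notes that controlled human data are lacking, and sets precautions that continue after the last dose. The collection rule does not follow those precautions past exit. A pregnancy that begins inside the post-dose contraception period is one the protocol tries to prevent, but if it happens the site has no general instruction to record it.

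For pregnancies beginning after exit, three kinds have no collection rule: uncomplicated pregnancies, which form the denominator for any outcome; abnormal outcomes judged unrelated to the product; and complications or elective terminations that do not amount to a related SAE. Section 8.3.5.1 collects all of these when the pregnancy begins during the study. At stake is the completeness of safety data on a named ESI. The efficacy analysis is not affected.

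**Working it through.** The plan states no figure on this point, so there is none to reproduce. The check compares dates.

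**Inputs**
- Contraception period after last dose: 4 weeks = 28 days (women), 12 weeks = 84 days (men); Sections 5.1 and 5.3.1.
- Exit: Visit 4, Day 43 ± 3, so Day 40 to 46; Section 8.1.5.
- Last dose, reading A: at Visit 4 in the clinic, after the 08:00 IOP; Schedule of Activities and Sections 6.4, 8.1.4 and 8.1.5.
- Last dose, reading B: the day before Visit 4. Section 6.2.2 ends dosing with the morning before Visit 4, and SAP Section 4.1.2 uses the day before Visit 4 when the last-dose date is missing.

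**Formula**

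Uncovered days = (last-dose day + contraception period) − exit day.

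**Completer exiting on Day 43**

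| Reading | Group | End of period | Uncovered days |
|---|---|---|---|
| A (last dose Day 43) | Women | 43 + 28 = Day 71 | 71 − 43 = 28 |
| A | Men's partners | 43 + 84 = Day 127 | 127 − 43 = 84 |
| B (last dose Day 42) | Women | 42 + 28 = Day 70 | 70 − 43 = 27 |
| B | Men's partners | 42 + 84 = Day 126 | 126 − 43 = 83 |

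Moving exit to Day 40 or Day 46 moves both dates together and leaves the uncovered days unchanged. Routine collection therefore covers 0 to 1 of 28 days and 0 to 1 of 84 days.

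As a share of the whole span from Day 1 to the end of the period, the uncovered part is:
- women: 27/73 = 37% (exit Day 46, reading B) to 28/68 = 41% (exit Day 40, reading A);
- men's partners: 83/129 = 64% to 84/124 = 68%, for the same two cases.

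**Subject who stops drug early but stays under observation (Section 7.1)**

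Here exit comes later than the last dose, so part of the period is covered. As an illustration, take a last dose on Day 15 and exit on Day 43. The subject is in the study for 43 − 15 = 28 days after the last dose. Sections 8.3.5.1 and 8.3.5.2 then cover 28 of 28 days for a woman and 28 of 84 for a man's partner, leaving 56. Under the during-treatment wording of Section 8.2.2.10, none of those days would count. The two triggers therefore give different answers for the same subject.

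**Which pregnancies fall outside**

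Sections 8.3.5.1 and 8.3.5.2 turn on when the pregnancy begins, and their 24-hour reporting clock starts when the site learns of it. A conception before exit that comes to light afterwards is therefore in scope. The Visit 4 procedures do not ask the subject to report one, so the rule has no stated means of reaching the site. A conception after exit is out of scope, apart from the related-SAE route.

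**The case against.** The strongest reply is that the gap is narrow and partly guarded. Contraception is part of eligibility, and urine tests are done at screening, baseline and Visit 4. In-study pregnancies are followed to outcome, and related pregnancy SAEs must be reported even after the study. The sponsor may also request follow-up past exit. The trial has about 100 subjects treated for six weeks with a topical product. All of this stands, and it keeps the severity low. It does not supply a rule for an uncomplicated pregnancy, or one with an outcome judged unrelated, that begins after exit.

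Four stronger readings are tempting, and the documents do not support them.

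- A reader might infer that pregnancies conceived late in dosing and found after exit are not collected, and try to estimate what share the Visit 4 test would miss. The trigger is the start of the pregnancy, so these are already covered. The documents also give no detection lag from which to work out such a share.
- A reader might treat the 4 and 12 weeks as periods of fetal exposure. The protocol calls for contraception over them and does not describe them as exposure periods.
- A reader might conclude from the differing follow-up end points that congenital anomalies could be lost. Section 8.2.2.10 refers pregnancy follow-up to Section 8.3.5, where the neonate is followed and anomalies are SAEs. The difference is one of wording.
- A reader might say that nobody has any post-dose coverage. That is true, to within a day, only of completers.

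The consent form itself is not among the documents, so it may already ask subjects to report later pregnancies.

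**Conclusion.** The point holds in this limited form. For completers, 27 to 28 of 28 days (women) and 83 to 84 of 84 days (men's partners) of the protocol's contraception periods have no routine pregnancy collection. Pregnancies that began before exit are within the rule but lack a prompt to report them.

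The day counts rest only on the visit schedule and the stated periods; the one-day range comes from the conflicting descriptions of the last dose. The number of pregnancies that would go unrecorded cannot be computed, because the documents give neither the number of women of childbearing potential nor a pregnancy rate. It is assumed to be small. Severity is low: this is an inexpensive improvement to safety data on a named ESI.

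**What to change.** 1. In Sections 8.3.5.1, 8.3.5.2 and 8.2.2.10, extend passive pregnancy reporting to pregnancies that begin within the post-dose periods already stated in criterion 3 for women and for men.
2. In Section 8.1.5, have the site ask each subject at Visit 4 to report any such pregnancy, including one that began before exit and is recognised later. Check whether the consent form already says this.
3. Have Section 8.2.2.10 point to Section 8.3.5 for both the reporting trigger and the follow-up end point, so that each is stated once.
4. Reconcile Sections 5.1 and 5.3.1 with Section 8.2.2.10 on the force of the post-dose contraception wording and on whether the period counts from last dose or study completion. Reconcile Section 6.2.2 with Sections 8.1.4 and 8.1.5 on the day of the last dose. The reporting period should follow the reconciled text.

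The cost is protocol wording, and consent wording if the request is missing there. No visit, test or new form is added. The downside is that a passive site contact stays open for up to 12 weeks after exit.
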